6.7.4. Vital Signs

The analyses described below will be conducted for the following vital signs assessments respectively:

- SBP (mmHg)
- DBP (mmHg)
- Heart Rate (bpm)
- Respiratory Rate (breaths/min)
- Body Temperature (°C)

In accordance with the baseline value definition in Section 5.1.2, the change from baseline will be derived as follows:

Change (unit) = (post-baseline value – baseline value)

The following will be summarized for the Safety Analysis Set:

• Observed values and change from baseline at each assessed timepoint (Week 1, 2, 3, 4, 8, 12, 13,14, 15,16, 17 18, 20, 24, 28, 32, and 39) for each standard vital sign parameter using default summary statistics for continuous variables.

A listing of all vital signs data including derived change from baseline will be provided for the Safety Analysis Set.

6.7.5. Electrocardiograms

The following electrocardiogram (ECG) assessments will be taken at baseline, Weeks 16, 32 and 39:

- An overall assessment classified as normal or abnormal
- Abnormal assessments will be further classified as clinically significant or not clinically significant

At baseline assessment, the subject will be classified as abnormal if any (one or more) of the replicate assessments are classified as abnormal. Similarly, the abnormal assessment will be classified as clinically significant if any (one or more) abnormal assessments are classified as clinically significant. The subject will be classified based on the worst finding of triplicate 12-Lead ECG. A list of ECG assessments will be presented.

6.7.6. Physical Examination

Clinically significant findings observed prior to the first dose of study drug will be entered on the CRF in medical history in the CRF and reported as medical history. Clinically significant findings observed after the first dose of study drug will be reported as AEs in the CRF and reported as AEs.

For each physical examination body system, the number and percentage of subjects with abnormalities at baseline and at each assessed timepoint (Screen and Week 32) will be summarized for the Safety Analysis Set.

Physical examination findings (normal/abnormal/clinically significant) and details of abnormalities will be listed for each subject at each assessment timepoint (Screen and Week 32).

6.7.7. C-SSRS

Suicidal ideation and behavior will be assessed during the study (Screen, Week 0, 4, 8, 12, 16, 20, 24, 28, 32, and 39) by trained study personnel using the C-SSRS. C-SSRS evaluates suicidal ideation (Category 1 - Category 5) and behavior (Category 6 - Category 10). The following outcomes are C-SSRS categories and have binary responses (yes/no).

- Category 1 Wish to be Dead
- Category 2 Non-specific Active Suicidal Thoughts
- Category 3 Active Suicidal Ideation with Any Methods (Not Plan) without Intent to Act
- Category 4 Active Suicidal Ideation with Some Intent to Act, without Specific Plan

Final, Version 3.0, 03APR2024 Page 63 of 75 ST-AD-008 version 06

- Category 5 Active Suicidal Ideation with Specific Plan and Intent
- Category 6 Preparatory Acts or Behavior
- Category 7 Aborted Attempt
- Category 8 Interrupted Attempt
- Category 9 Actual Attempt (non-fatal)
- Category 10 Completed Suicide

At the screen visit, the C-SSRS will be listed by lifetime and past 6 months from suicidal ideation, and lifetime and past two years from suicidal behavior for each category. At the post-screen visit, the C-SSRS will be listed as since the last visit for each category.

6.7.8. Interim Analysis and Data Monitoring

An independent Data Monitoring Committee (DMC) will be established to monitor data on an ongoing basis to ensure the continuing safety of the subjects enrolled in this study.

The DMC will consist of at least one medical expert with the relevant therapeutic area and at least one statistician. The DMC will also have a minimum of three members, one of whom will serve as the Chair. The DMC responsibilities, authorities, and procedures will be documented in the DMC charter. The committee will meet approximately every 6 months to review interim data. After each review, the DMC will make recommendations regarding the continuation of the study based on safety. In addition, the DMC will meet as indicated below to review data from Part A and Part B.

Part A

The DMC will review data in Part A after all subjects have had the opportunity to complete the Week 8 visit (or discontinued the study early). Based on this review, the DMC may recommend continuing, stopping, or altering Part B.

Part B

In Part B, no formal interim analysis is planned for purposes of stopping or altering this study. The DMC will review unblinded data when the first approximately 105 subjects randomized into Part B have had the opportunity to complete the Week 8 visit to make a recommendation on further development activities for izokibep. The DMC will not be empowered to recommend stopping this study or changing the sample size due to a demonstration of positive efficacy. The type I error rate for hypothesis tests at the end of the study will be decreased by 0.0001 to account for this interim summary of unblinded data. The study team and the investigators will remain blinded to these interim results until after the study is completed.

After all subjects have had an opportunity to complete the Week 16 visit (complete the visit, or complete a subsequent visit, or permanently discontinue the study), the primary endpoint analyses may be conducted. These will be the final analyses for the primary endpoint, so no

adjustment of the type I error will be applied. Site staff, and all Sponsor staff who interact with site staff, will remain blinded to individual subject treatment assignment until the final subject has completed the final visit.

6.8. Pharmacokinetic Assessments

Pharmacokinetic data will be summarized by treatment group and scheduled visit, including N (number of non-missing data), N BLQ (for concentrations only), arithmetic mean, standard deviation (SD), arithmetic coefficient of variation (CV%), geometric mean, geometric CV%, median, minimum, and maximum. Only trough collections are planned, so no calculations of PK parameters (maximum concentration, area under the concentration curve, etc.) will be provided.

For the calculation of summary statistics, pre-dose concentrations that are below the limit of quantification (BLQ) will be treated as zero and post-dose concentrations that are BLQ will be treated as missing.

Pharmacokinetic data may be combined with data from other studies of izokibep for modeling. If this is done, details will be described in a separate document.

6.9. Anti-Drug Antibodies

Samples tested for ADAs will be reported as positive or negative based on a non-specific screening assay. Samples that are positive, and are further tested, will be reported as positive or negative for the IL-17A binding domain, positive or negative for the albumin binding domain, and/or positive or negative as a neutralizing ADA. Any continuous values of concentration (titers) will be summarized using observed data.

Subjects will be summarized at each scheduled visit according to the screening test, with number (%) positive. Positive samples on the screening test, that are further tested, will be reported according to each specific binding domain, with number (%) positive for the IL-17A binding domain, number (%) positive for the albumin binding domain, and number (%) positive for either (one or both) binding domain. Samples that are further tested on a neutralizing antibody assay will be reported as number (%) positive for neutralizing activity, with percentage calculated using the number that were positive according to the screening test as the denominator.

7. Appendices

Document Version, Status, Date	Summary/Reason for Changes	
Version 1, Final, 10FEB2023	Not applicable; the first version	
Version 2, Final, 19JUN2023	Updated according to Protocol V3, 26APR2023	
Version 3, Final, 03APR2024	Updated to include additional details on post-Week 16 efficacy and safety analyses; updated handling of BLQ for PK to align with other studies in the program; added clarity to definitions of Period 1 and Period 2; updated Appendix 2 scoring rules and added clarity to align with verified approach	

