To assess the safety and tolerability of izokibep as measured by the incidence of TEAEs, events of interest, SAEs, and clinically significant laboratory values and vital signs	 TEAEs, events of interest, and SAEs Laboratory values and vital signs at collected timepoints 			
To assess the immunogenicity of izokibep as measured by the presence of ADAs	• ADAs			
Exploratory				
Part B				
To explore if one or both regimens of izokibep is efficacious, as measured by:				
• Percentage of subjects who achieve HiSCR75 ¹ at Weeks 2, 4, 8, 12, and 32.	• HiSCR75 ¹ at Weeks 2, 4, 8, 12, and 32			
Percentage of subjects who achieve HiSCR90¹ at Weeks 2, 4, 8, 12, and 32	• HiSCR90 ¹ at Weeks 2, 4, 8, 12, and 32			
Percentage of subjects who achieve HiSCR100¹ at Weeks 2, 4, 8, 12, and 32	• HiSCR100 ¹ at Weeks 2, 4, 8, 12, and 32			
Percentage of subjects who achieve HiSCR50¹ at Weeks 2, 4, 8, 12, and 32	• HiSCR50 ¹ at Weeks 2, 4, 8, 12, and 32			
Percentage of subjects with baseline Hurley Stage II who achieved AN count of 0, 1, or 2 at Weeks 4, 8, 12, 24, and 32	• AN count of 0, 1, or 2 at Weeks 4, 8, 12, 24, and 32			
NRS Patient Global Assessment of Skin Pain from baseline after 4, 8, 12, 16, 24, and 32 weeks of treatment	Change in pain score from baseline at Weeks 4, 8, 12, 16, 24, and 32			
Modified Sartorius Score after 4, 8, 12, 16, 24, and 32 weeks of treatment	Modified Sartorius Score at baseline, Weeks 4, 8, 12, 16, 24, and 32			
HS flare rates through 4 and 32 weeks of treatment	HS flares through Weeks 4 and 32			

Objectives	Endpoints
• IHS4, after 4, 8, 12, 16, 24, and 32 weeks of treatment	• IHS4 scores at Weeks 4, 8, 12, 16, 24, and 32
Hidradenitis Suppurativa-Physician's Global Assessment (HS-PGA)	Change from baseline to Week 16 in HS-PGA
To explore the effect of izokibep on PROs as measured by change from baseline over time in: • EQ-5D	• Change from baseline to Week 16 in EQ-5D
• DLQI	Change from baseline to Week 16 in DLQI
• HADS	Change from baseline to Week 16 in HADS, HADS-anxiety and HADS-depression
To evaluate the pharmacokinetics of izokibep in subjects with HS	Trough plasma concentrations of izokibep at collected timepoints

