8.7. Immunogenicity Assessments

- Antibodies to izokibep will be evaluated in serum samples collected from all subjects according to the SoA (Section 1.3). Additionally, serum samples should also be collected at the final visit from subjects who discontinued study drug or were withdrawn from the study. These samples will be tested by the sponsor or sponsor's designee.
- Instructions for the collection and handling of biological samples will be provided in the Laboratory Manual by the sponsor or designee.
- Samples testing positive for binding antibodies may be further characterized and may be tested for neutralizing antibodies.
- The detection and characterization of antibodies to izokibep will be performed using a validated assay method by or under the supervision of the sponsor.
- Antibody samples collected may be used for assay validation and related assay development purposes.
- Anti-drug antibodies (ADA) serum samples will be shipped frozen from clinical sites to the central laboratory and later shipped from the central laboratory to the ADA laboratory for analysis. The ADA serum samples will be stored in a secure storage space with adequate measures to protect confidentiality.
- Samples will be retained while research on izokibep or study drugs of this class or HS continues but no longer than 20 years or other period as per local requirements.

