2.8. Immunogenicity

Antibodies to izokibep will be evaluated in serum samples collected from all subjects according to the SoA in the protocol. These samples will be tested by the sponsor or sponsor's designee.

Samples may be further tested for IL-17A binding domain and albumin binding domain (positive vs negative) and/or in a neutralizing antibody assay.

3. Estimands

The ICH¹ E9 (R1) addendum on estimands² and sensitivity analysis in clinical trials to the guideline on statistical principles for clinical trials came into effect on 30 July 2020. This section addresses the construction of estimands for the primary, secondary, and exploratory objectives. Each estimand is defined according to the following five attributes:

- The **treatment** condition of interest, and as appropriate, the alternative condition to which comparison will be made.
- The **population** of subjects targeted by the clinical question.
- The **variable** (or endpoint) to be obtained for each subject that is required to address the clinical question.
- The clinical question of interest in respect of **other intercurrent events** not covered through the precise specifications of treatment, population and variable.
- A **population-level summary** for the variable providing a basis for comparison between treatment conditions.

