4.5. ADA Analysis Set

The ADA analysis set for subjects in Part A and Part B will include all subjects who received at least 1 administration of test material (izokibep or placebo) and have both baseline ADA and at least 1 post-dose ADA measurement.

5. Data Handling

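### The neutralizing-antibody percentage in SAP 6.9 is only a lower bound if any screening-positive sample goes untested, and the ADA summary does not separate pre-existing from treatment-emergent antibodies

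*SAP*

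**What the plan says.** **Neutralizing antibodies.** SAP 6.9 defines the summary in one sentence. Its first half sets the numerator: "Samples that are further tested on a neutralizing antibody assay will be reported as number (%) positive for neutralizing activity". Its second half sets the base: "with percentage calculated using the number that were positive according to the screening test as the denominator".

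Three places make further testing conditional:

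- Protocol 8.7: "Samples testing positive for binding antibodies may be further characterized and may be tested for neutralizing antibodies".
- SAP 2.8: "Samples may be further tested for IL-17A binding domain and albumin binding domain (positive vs negative) and/or in a neutralizing antibody assay".
- SAP 6.9, on binding domains: "Samples that are positive, and are further tested, will be reported as positive or negative for the IL-17A binding domain".

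Neither document requires every screening-positive sample to be tested, gives a rule for choosing which are tested, provides a category for samples not tested, or commits to reporting the number tested.

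**Presence of ADA.** Protocol Section 3 makes immunogenicity a secondary objective. For Part B the wording is "To assess the immunogenicity of izokibep as measured by the presence of ADAs". SAP 6.9 addresses it this way: "Subjects will be summarized at each scheduled visit according to the screening test, with number (%) positive". SAP 4.5 admits to the ADA set only subjects who "have both baseline ADA and at least 1 post-dose ADA measurement". SAP 6.9 contains no within-subject comparison of later results with the baseline result.

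**The concern.** The neutralizing percentage has a numerator and a denominator drawn from different groups of samples. A screening-positive sample that is not sent to the neutralizing assay enters the denominator and can never enter the numerator. If such samples exist, the printed percentage mixes how often antibodies neutralize with how often the laboratory looked. Without the number tested, a reader cannot separate the two, and the error, where there is one, is in the reassuring direction.

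The ADA summary raises a different question. Visit-by-visit positivity gives the overall proportion positive on Day 1 and at each later visit. It does not show whether the subjects positive later are those who were already reactive before izokibep. SAP 6.9 itself describes the screening assay as non-specific, so reactivity before exposure is plausible. For subjects randomized to placebo, Day 1 is also not the last sample before izokibep, because they switch at Week 16.

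**Working it through.** The documents state no figure on this point, so there is nothing to reproduce.

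**Definitions.** Let S be the number of screening-positive samples, T the number of those tested for neutralization (T ≤ S), and X the number found neutralizing (X ≤ T). Write f = T/S for the fraction tested and p = X/T for the rate among tested samples.

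**Formulas.**

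- Percentage under SAP 6.9: X/S = f × p.
- Percentage on tested samples: X/T = p.
- True rate among all S, with the S − T untested results unknown: at least X/S (no untested sample neutralizes) and at most (X + S − T)/S (all of them do).

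The SAP percentage is therefore always the lower bound. It equals the tested-sample rate when f = 1 (or trivially when X = 0). It equals the true rate among screening positives when f = 1 or when every untested sample is truly non-neutralizing.

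**Illustration.** The documents give neither f nor p. Assume S = 40 and p = 30%:

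| Tested (T) | Neutralizing (X) | SAP 6.9: X/S | Tested samples: X/T | Possible true rate among all 40 |
|---|---|---|---|---|
| 40 | 12 | 30.0% | 30% | 30.0% |
| 30 | 9 | 22.5% | 30% | 22.5% to 47.5% |
| 20 | 6 | 15.0% | 30% | 15.0% to 65.0% |
| 10 | 3 | 7.5% | 30% | 7.5% to 82.5% |

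For example, the upper limit in the third row is (6 + 40 − 20)/40 = 65%. With p = 10% the SAP percentage is 7.5%, 5% and 2.5% at f = 75%, 50% and 25%; with p = 50% it is 37.5%, 25% and 12.5%.

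**The opposite error.** Keep S = 40, T = 20 and X = 6, but suppose all 20 untested samples are truly non-neutralizing. The true rate is 6/40 = 15%, so the SAP percentage is right and the tested-sample figure of 6/20 = 30% is too high. Neither denominator is safe alone when selection for testing is related to the result.

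**Presence of ADA.** No arithmetic applies. The protocol's Schedule of Activities places ADA samples at Day 1 and Weeks 2, 4, 8, 12, 16, 24, 32, 39 and 45, drawn pre-dose on dosing days (footnote m). For subjects starting izokibep on Day 1, the Day 1 sample precedes exposure. For subjects switching from placebo, the Week 16 pre-dose sample is the last before exposure. A within-subject comparison is therefore possible from planned data; SAP 6.9 does not ask for it.

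**The case against.** Several objections have force.

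- Optional wording permits testing every positive as readily as testing a few, and if all are tested there is no discrepancy. This stands, and it makes the problem conditional.
- No sentence classifies an untested sample as negative. The percentage can be read as demonstrated neutralizing activity among screening positives, with the screening-positive count visible. That reading is legitimate, but SAP 6.9 does not label the figure that way, and the number tested is still not promised.
- The stated objective is the presence of ADAs, and neutralization is further characterization. This stands: the denominator issue does not touch the screening-positivity summary.
- Day 1 is a scheduled ADA visit, so baseline positivity should appear beside later visits, and baseline data define the ADA set. A reader might infer that baseline is ignored altogether; the documents do not support that. What is missing is the subject-level change from negative to positive.
- SAP 6.1 lets the table shells set denominators, and the shells are outside the two documents. They may show the number tested, but that would not change the explicit denominator in SAP 6.9.

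A reader might also infer that the neutralizing rate will be understated by exactly the untested share. That holds only if selection for testing is unrelated to neutralizing status, and neither document says how samples are selected.

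**Conclusion.** The point holds in conditional form. As written, SAP 6.9 gives a lower bound on the neutralizing rate among screening positives whenever any positive sample is untested, and that figure is too low unless all untested samples are truly non-neutralizing. The size cannot be computed from the documents; every fraction and rate in the illustration is an assumption. It would be tempting to conclude that the tested-sample denominator is simply the correct one. The 15% against 30% example shows that it is not: it represents all positives only when selection is unrelated to neutralization.

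The second part holds too. By-visit positivity does not separate pre-existing from treatment-emergent ADA within subjects, although SAP 4.5 requires the baseline result needed to do so.

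Both parts concern descriptive summaries for a secondary objective. No hypothesis test uses them.

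**What to change.** In SAP 6.9:

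1. Report the number screening-positive, the number tested for neutralization and the number not tested. Give the neutralizing percentage on tested samples, and show the screening-positive percentage labelled as a lower bound. State the rule for choosing samples, and note that the tested-sample figure represents all positives only if that choice is unrelated to neutralization. Alternatively, commit to testing every screening-positive sample, in which case the two percentages agree.
2. Add the number (%) of subjects ADA-negative before their first izokibep dose and positive at any later sample. Use Day 1 as baseline for subjects starting on izokibep and the Week 16 pre-dose sample for those switching from placebo. Show subjects positive at that baseline separately, with titers where available. Present the count by randomized group: nine ADA samples are scheduled after Day 1, but only four after Week 16 (Weeks 24, 32, 39 and 45).
3. While editing, state the denominator for the binding-domain percentages, which SAP 6.9 leaves open, and say whether each percentage counts subjects or samples.

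The cost is SAP wording and table changes. The reporting option and the new count need no extra visit or blood sample. The option of testing every positive adds laboratory assays for any samples that would otherwise go untested.

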Appendix 1: Document History

Appendix 2: End Points Definitions and Scoring Method Modified Sartorius Score⁸

The modified Sartorius score includes an assessment of the anatomical regions involved, the numbers and scores of lesions for each region, the longest distance between 2 relevant regions (or size of a single lesion), and whether all lesions are separated by normal skin (yes or no). The detailed scoring is as following:

Each region will score as:

Item No	Items	Scoring Rules	Points	Score:
1	Anatomical region	If the region is affected	3	
		If the region is not affected, the score for that region is 0, and no further calculations are needed for the region. If the region is affected, the following are added in addition to the 3 points for the region in line 1 above.		
	For each affected region:			
2	Nodules (Inflammatory)	Count from this region	1	$1 \times \text{count}$
3	Fistulae (Draining only)	Count from this region	6	$6 \times \text{count}$

4	Longest distance between two relevant lesions within a region or size of the lesion if single	< 5 cm	1	
		5 - 10 cm	3	
		> 10 cm	9	
5	Lesions separated by normal skin?*	Yes	0	
		No	9	
	Score for the region			Sum of above

* If Lesions separated by normal skin = "No" and/or Hurley Stage = "STAGE III" then 9 points is added for the region.

Score for each region is (if the region involved) = $3 + (number of inflammatory nodule) \times 1$ + {(number of draining fistula) × 6 + {0 < (The longest distance between two relevant lesions [or size of lesion if single]) <5} × 1+ {5≤(The longest distance between two relevant lesions [or size of lesion if single]) ≤ 10} × 3 + {(The longest distance between two relevant lesions [or size of lesion if single]) > 10} × 9 + (all lesions separated by normal skin = Yes or Hurley Stage = "STAGE III") × 9

Modified Sartorius score is the sum of the score of each region. Any region with no involvement will have a score of zero for purposes of calculating the modified Sartorius score.

A region is considered "affected" if any of the following conditions are true:

- Abscess Count > 0 OR
- Any "Interventions needed" questions response = YES
- Any "Interventions needed DATE" question is not missing.
- Any "How many lesions had intervention" question > 0
- Any "How many lesions had intervention AND are no longer present" > 0
- Non-draining fistula count > 0
- Draining fistula count > 0
- Non-inflammatory nodule count > 0

- Inflammatory nodule count > 0
- Hypertrophic scar > 0
- Longest distance > 0
- Normal appearance tissue = NO Hurley Stage contains "STAGE"

EQ-5D⁹

The EQ-5D descriptive system comprises the following 5 dimensions: mobility, self-care, usual activities, pain/discomfort, and anxiety/depression. Each dimension has 3 levels: no problems, some problems, and extreme problems. A unique health state is defined by combining 1 level from each of the 5 dimensions. There are 243 possible health states defined in this way. Each state is referred to in terms of a 5-digit code. No health state value will be calculated if any of the dimensions are missing.

Domain Scores of EQ-5D-3L Descriptive System

Response Category	Score
No problems	1
Moderate problems	2
Severe problems	3

Note: Missing values are coded as '.'. Ambiguous values (e.g., 2 boxes are ticked for a single dimension) should be treated as missing values.

EQ-5D-3L = sum(non-missing question score)/(number of non-missing questions) \times 5. If the number of questions with a missing answer is \geq 3 (\geq 50%) then EQ-5D-3L is missing.

For example, if a patient provides the following responses: Mobility = No problems, Self-care = No problems, Usual Activities = Moderate problems, Pain/Discomfort = Moderate problems, Anxiety/Depression = Extreme problems, his response sequence is 11223. The 243 theoretical possible sequences can then be mapped to an index value to provide a summary across all dimensions. For the calculation of the index value, the UK value set based on Time Trade-Off method will be used. The scoring algorithm is as follows:

Full health (11111) =	1.000
At least one domain at 2 or 3 (N2): At least one domain at 3 (N3):	-0.081 -0.269
Mobility level 1:	0

Mobility level 2:	-0.069
Mobility level 3:	-0.314
Self-care level 1:	0
Self-care level 2:	-0.104
Self-care level 3:	-0.214
Usual activities 1:	0
Usual activities 2:	-0.036
Usual activities 3:	-0.094
Pain/discomfort 1:	0
Pain/discomfort 2:	-0.123
Pain/discomfort 3:	-0.386
Anxiety/depression 1:	0
Anxiety/depression 2:	-0.071
Anxiety depression 3:	-0.236

The index for the patient with example sequence 11223 = 0.255, calculated as follows:

Full health = 1

Minus N2: -0.081

Minus N3: -0.269

Minus mobility level 1:0

Minus self-care level 1:0

Minus usual activities level 2: -0.036

Minus pain/discomfort level 2: -0.123

Minus anxiety/depression level 3: -0.236

where level 1 corresponds to no problems, level 2 to some problems and level 3 to extreme problems.

DLQI¹⁰

DLQI measures the health-related quality of life of adult patients suffering from a skin disease. It comprises 10 items arranged in six categories: symptoms and feelings (questions 1 and 2), daily activity (3 and 4), leisure (5 and 6), work or study (7), interpersonal relationships (8 and 9), and treatment (10). The total score can vary from 0 (no impact) to 30 (maximum impact). The DLQI score is calculated by summing the score of each question resulting in a maximum of 30 and a minimum of 0. The highest score represents the highest impairment of the health-related quality of life.

The scoring of each question is as follows:

• Very much	Scored 3
• A lot	Scored 2
• A little	Scored 1
• Not at all	Scored 0
• Not relevant	Scored 0
Question unanswered or missing	Scored 0
• If leading Question 7 response is Yes*	Scored 3
• If leading Question 7 response is not Yes*	Scored as above using follow- up Question 7

* Questions 7 and 7a substitute each other. Only 1 of them may contribute to overall DLQI both in terms of score and number of questions. I.e. if Q7 = "Yes" and Q7a = "A little" – only Q7 is scored as "3" and +1 non missing-question, while Q7a is completely ignored.

 $DLQI = sum(non-missing question score) / (number of non-missing questions) × 10. If the number of questions with a missing answer is <math>\ge 5$ ($\ge 50\%$) then DLQI is missing.

HADS¹¹

The HADS is a self-report rating scale of 14 items on a 4-point Likert scale (range 0-3, with 0 least severe and 3 most severe). It is designed to measure anxiety and depression (7 items for each subscale). The total score is the sum of the 14 items, and for each subscale, the score is the sum of the respective seven items (ranging from 0-21). HADS-Anxiety includes questions 1, 3, 5, 7, 9, 11, and 13. HADS-Depression includes questions 2, 4, 6, 8, 10, 12, and 14.

HADS will be present as anxiety, depression, and overall respectively. If the number of questions with a missing answer is ≥ 4 , ≥ 4 , and ≥ 7 ($\ge 50\%$) for anxiety, depression, and overall respectively, then the score is missing.

Erythema Score

At every visit, for each anatomic region affected by HS, the investigator will assess the overall degree of erythema using a four-point ordinal scale ranging between 0 and 3.

- Left axilla
- Right axilla
- Left sub/inframammary area
- Right sub/inframammary area
- Intermammary area
- Left buttock

- Right buttock
- Left inguino-crural fold
- Right inguino-crural fold
- Perianal
- Perineal
- Upper Back and Neck
- Other

The scoring rule as following:

- 0 =no redness
- 1 = faint but discernible pink coloration
- 2 = moderate red coloration
- 3 = very red or bright red coloration

Erythema score = $12 \times \{\text{sum (non-missing score of each region [total 12 regions + Other regions]})/ (number of non-missing region)\}. The multiplier of 12 will not change even if the number of non-missing + Other regions changes. If the number of questions with a missing answer is <math>\geq 6 (\geq 50\%)$ then the Erythema score is missing.

A region is considered "affected" if it has a > 0 abscess/nodule/fistula count or a non-zero response to any of the other quantitative questions on the Lesion Count/Hurley Stage eCRF form for the region or "intervening normal appearance tissue" = "No" or Hurley Stage not equal to "Not Applicable".

SF-12v2

The SF- $12v2^{12}$ is a self-reported outcome measure assessing the impact of health on an individual's everyday life. Two component scores are derived from the SF-12 including the SF-12 Physical Component Score and the SF-12 Mental Component Score. SF-12 summary score can be calculated only when all components are non-missing (i.e. all answers provided), otherwise should be set to missing. If all answers are available then calculate as per following steps.

The instructions for computing the component scores are as follows:

- 1. Compute raw scale scores based on the table from precoded item value to final item value.
- 2. Transform raw scale scores to 0-100 scale.
- 3. Standardization of SF-12v2 scales (Z-scores), Standard Form
- 4. Norm-Based Transformation of SF-12v2 scales Z-scores, Standard Form
- 5. Norm-Based Scoring SF-12v2 Physical and Mental Summary Measures

1. Precoded and final values by items:

Item: 1

Response choices	Precoded Item Value	Final Item Value
Excellent	1	5.0
Very good	2	4.4
Good	3	3.4
Fair	4	2.0
Poor	5	1.0

Items: 2a, 2b

Response choices	Precoded Item Value	Final Item Value
Yes, limited a lot	1	1
Yes, limited a little	2	2
No, not limited at all	3	3

Items: 3a, 3b, 4a, 4b, 7

Response choices	Precoded Item Value	Final Item Value
All of the time	1	1
Most of the time	2	2
Some of the time	3	3
A little of the time	4	4
None of the time	5	5

Item: 5

Response choices	Precoded Item Value	Final Item Value
Not at all	1	5
A little bit	2	4
Moderately	3	3
Quite a bit	4	2
Extremely	5	1

Items: 6a, 6b

Response choices	Precoded Item Value	Final Item Value
All of the time	1	5
Most of the time	2	4
Some of the time	3	3
A little of the time	4	2
None of the time	5	1

Items: 6c

Response choices	Precoded Item Value	Final Item Value
All of the time	1	1
Most of the time	2	2

Statistical Analysis Plan

Some of the time	3	3
A little of the time	4	4
None of the time	5	5

2. Transformation of scale scores:

The next step involves transforming each raw score to 0-100 scale using the formula shown below:

```
Transformed scale = \left[\frac{(Actual raw score - lowest possible raw score)Possible raw score range}{100}\right] \times 100
```

This transformation converts the lowest and highest possible scores to zero and 100, respectively. Scores between these values represent the percentage of the total possible score achieved.

Scale items aggregated and range of possible scores:

SF-12v2 scale	Sum final Item Values (after recoding items)	Lowest and highest possible raw scores	Possible raw score range
Physical Functioning (PF)	Items 2a + 2b	2, 6	4
Role Physical (RP)	Items 3a + 3b	2, 10	8
Bodily Pain (BP)	Item 5	1, 5	4
General Health (GH)	Item 1	1, 5	4
Vitality (VT)	Item 6b	1, 5	4
Social Functioning (SF)	Item 7	1, 5	4
Role Emotional (RE)	Items $4a + 4b$	2, 10	8
Mental Health (MH)	Items 6a + 6c	2, 10	8

1. Standardization of SF-12v2 scales (Z-scores), Standard Form:

Formulas for z-score standardization of SF-12v2 scales, Standard Form:

SF-12v2	Z-scores
Physical Functioning (PF_Z)	$PF_Z = (PF - 81.18122) / 29.10558$
Role Physical (RP_Z)	$RP_Z = (RP - 80.52856) / 27.13526$
Bodily Pain (BP_Z)	$BP_Z = (BP - 81.74015) / 24.53019$
General Health (GH_Z)	$GH_Z = (GH - 72.19795) / 23.19041$
Vitality (VT Z)	VT $Z = (VT - 55.59090) / 24.84380$
Social Functioning (SF_Z)	$SF_Z = (SF - 83.73973) / 24.75775$
Role Emotional (RE_Z)	$RE_Z = (RE - 86.41051) / 22.35543$

Mental Health (MH_Z)	$MH_Z = (MH - 70.18217) /$
	20.50597

Norm-Based Transformation of SF-12v2 scales Z-scores, Standard Form:

SF-12v2	Norm-Based scores
Physical Functioning (Norm-Based PF)	Norm-Based $PF = 50 + (PF_Z * 10)$
Role Physical (Norm-Based RP)	Norm-Based $RP = 50 + (RP_Z * 10)$
Bodily Pain (Norm-Based BP)	Norm-Based BP = $50 + (BP_Z * 10)$
General Health (Norm-Based GH)	Norm-Based $GH = 50 + (GH_Z *$
	10)
Vitality (Norm-Based VT)	Norm-Based VT = $50 + (VT Z * 10)$
Social Functioning (Norm-Based SF)	Norm-Based SF = $50 + (SF_Z * 10)$
Role Emotional (Norm-Based RE)	Norm-Based RE = $50 + (RE Z * 10)$
Mental Health (Norm-Based MH)	Norm-Based MH = $50 + (MH_Z *$
	10)

